# 6.12.2 Measurement of In Vitro Dystrophin Protein and Dystrophin mRNA (Skin Biopsy)

To investigate the reactivity of the muscle cells of each subject to DS-5141b, in vitro studies using skin fibroblasts will be performed. For subjects participating in this

study from Part 1 or Part 2, a skin sample will be collected at the time of muscle biopsy before the first dose of the study drug and stored (set temperature: 4°C) in a storage container prepared by the sponsor or central laboratory until it is submitted to the central laboratory. Details are specified in a separate procedure.

The investigator or subinvestigator will record whether skin biopsy was performed and the date of biopsy on the case report form.

# 6.12.3 Measurement of Blood Cell Dystrophin mRNA (Blood Collection [Whole Blood])

To measure the dystrophin mRNA induced by exon 45 skipping in blood cells, before the first dose of the study drug and after the last dose of the study drug at each dose level (Day 15 or at withdrawal) in Part 1 and before the first dose of the study drug and after the last dose of the study drug (Day 85 or at withdrawal) in Part 2, 2.5 mL of blood will be collected in the blood collection tube prepared by the sponsor or central laboratory and stored frozen (set temperature: ≤−20°C) until it is submitted to the clinical specimen storage facility contracted by the sponsor. Details are specified in a separate procedure.

The investigator or subinvestigator will record whether blood was collected and the blood collection day on the case report form.

#### 6.12.4 Measurement of Micro RNA (Blood Collection [Serum])

Micro RNA in blood (such as miR-1, miR-133, and miR-206) will be measured. Part of the serum obtained for measurement of anti-dystrophin antibody (see 6.10) will be used as the specimen. Details are specified in a separate procedure.

#### 6.12.5 Measurement of Urine Protein (Urine Collection)

To measure urine protein (such as titin), which is an indicator of muscle decomposition, before the first dose of the study drug and after the last dose of the study drug at each dose level (Day 15 or at withdrawal) in Part 1, before the first dose of the study drug and after the last dose of the study drug (Day 85 or at withdrawal) in Part 2, before the first dose of the study drug, on Week 13/ Day 85, Week 25/ Day 169, and Week 37/ Day 253 in Part 2-Extension, and before the first dose of the study drug, on Week 13/ Day 85, Week 25/ Day 169, Week 37/ Day 253 and after the last dose of the study drug (Week 49/ Day 337 or at withdrawal) in Part 2-Extension-2, 10 mL of urine will be collected in the urine collection tube prepared by the sponsor or central

laboratory and stored frozen (set temperature:  $\leq -70^{\circ}$ C) until it is submitted to the clinical specimen storage facility contracted by the sponsor. Details of the procedure and the measurement facility are specified separately.

The investigator or subinvestigator will record whether urine was collected and the urine collection day on the case report form.

# 6.12.6 Measurement of Blood DS-5141b Metabolites (Blood Collection [Plasma])

Unknown metabolites of DS-5141b will be exploratorily investigated. Part of the plasma obtained for pharmacokinetics (see 6.7) will be used as a specimen. Details are specified in a separate procedure.

# 6.12.7 Measurement of Urine DS-5141b Metabolites (Urine Collection)

To exploratorily investigate unknown metabolites of DS-5141b, before the first dose of the study drug in Part 1 and on the day after the last dose of the study drug at each dose level (Day 9 or at withdrawal), 5.0 mL of urine will be collected in a urine collection tube provided by the sponsor or central laboratory. The specimen will be stored frozen (set temperature: ≤−20°C) until it is submitted to the clinical specimen storage facility contracted by the sponsor. Details are specified in a separate procedure. The investigator or subinvestigator will record whether urine was collected and the urine collection day on the case report form.

# 6.13 Storage and Disposal of Specimens for Genetic Analysis and Biomarker Research

# 6.13.1 Storage of Specimens

In view of the possibility that, based on newly obtained knowledge, additional examinations of the relationship between the efficacy or safety of the study drug and the biomarkers will be performed, and that the above biomarkers will be measured again, the submitted specimens will be stored at the respective measurement facilities for up to 10 years from the time of the notification of the study plan for this study.

#### 6.13.2 Disposal of Specimens

All specimens that reach the end of their storage period will be disposed of by the biomarker measurement facility according to the instructions of the sponsor. If a subject withdraws consent for biomarker research, specimens will be disposed of according to the following procedures, depending on the location of the specimens at

that time. If biomarker analysis was performed at the measurement facility before the subject withdrew consent, this data will not be disposed of.

- If specimens are being temporarily stored at study site
   The investigator or subinvestigator will identify the specimens from the relevant subject and dispose of them.
- 2) If specimens are being stored at the clinical specimen storage facility The investigator or subinvestigator will inform the sponsor of the subject identification code of the relevant subject. The sponsor will instruct the clinical specimen storage facility to dispose of the relevant subject's specimens.

# 6.14 Long-Term Storage (Banking) of Clinical Specimens for Genomic and Genetic Analysis

Long-term storage (banking) of DNA specimens extracted from the subjects' blood will be performed, to enable genomic or genetic analysis relating to, for example, the efficacy or safety of DS-5141b. If research is performed using these DNA specimens, a research plan will be newly prepared.

# 6.14.1 Scope

At study sites where banking is approved, an explanation of banking will be provided, and samples obtained from subjects who provide informed consent based on this explanation will be included in the scope of banking. For subjects who provide informed consent for banking, the investigator or subinvestigator will record the date of informed consent on the case report form. If there is any information such as medical history that may affect genomic or genetic information (for example, allogeneic bone marrow transplantation), this will be recorded on the case report form.

# 6.14.2 Banking Specimens (DNA)

DNA will be extracted from some of the blood collected for checking the DNA sequence of the site of DS-5141b double-strand formation (see 6.8), and this will be used as the banking specimen.

# 6.14.3 Storage Period

The storage period of the banking specimens will be a maximum of 15 years from the date of submission of the notification of the study plan for this study.

# 6.14.4 Disclosure of the Result of Genomic and Genetic Analysis Using Banking Specimens

At present, the timing of pharmacogenomic investigation using banking specimens, the method of genomic or genetic analysis, and whether disclosure will be necessary are undetermined. Accordingly, we do not plan to disclose the result of genetic analysis to the investigator etc. and subjects.

# 6.14.5 Disposal of Banking Specimens

After the end of the storage period, or if a subject withdraws consent during the storage period, banking specimens will be promptly disposed of. However, if genetic analysis was performed before the end of the storage period or before consent was withdrawn, these data will not be disposed of.

#### 7. PHARMACOKINETIC ENDPOINTS

The following pharmacokinetic parameters will be calculated from the plasma DS-5141a (the free form of DS-5141b) concentration in Part 1, Part 2, Part 2-Extension, and Part 2-Extension-2 using a non-compartment model. Details of pharmacokinetic analysis will be specified in the Statistical Analysis Plan.

# <Pharmacokinetic parameters>

- Part 1 and Part 2 (first dose)
   Cmax, AUC168h, AUCinf, Tmax, Kel, t1/2, MRTinf, CL/F, Vz/F
- Part 2 (12th dose)
   Cmax, Cavg, AUCtau, Tmax, Kel, t1/2
- Part 2-Extension (48th dose) and Part 2-Extension-2 (48th dose)
   Cmax, Cavg, AUCtau, Tmax, Kel, t1/2, MRTinf, CLss/F, Vz/F, AR
- Part 2-Extension (first dose in subjects participating in the study from Part 2-Extension\*) and Part 2-Extension-2 (first dose in subjects participating in the study from Part 2-Extension-2\*)

Cmax, AUC168h, AUCinf, Tmax, Kel, t1/2, MRTinf, CL/F, Vz/F \*The 48th dose will be handled in the same way as for subjects continuing participation from Part 2

Since administration of the study drug was temporarily discontinued in Part 2-Extension, pharmacokinetic parameters for the 48th dose will be calculated only in cases where calculation is possible.

#### <Rationale>

These pharmacokinetic parameters were specified to assess the pharmacokinetics of single doses and repeated doses of DS-5141b, with reference to "Clinical Pharmacokinetic Studies of Pharmaceuticals."

# 8. EFFICACY ENDPOINTS

#### 8.1 Primary Endpoint

# 8.1.1 Expression of Dystrophin Protein in Muscle Tissue

Dystrophin protein will be measured by immunostaining, using frozen slices of muscle tissue. The expression of dystrophin protein will also be measured by the Western blot method using protein extracted from the muscle tissue.

# 8.2 Secondary Endpoint

# 8.2.1 Production of Exon 45-Skipped Dystrophin mRNA in Muscle Tissue

Using the total RNA extracted from muscle tissue, whether dystrophin mRNA induced by exon 45 skipping is produced will be measured with RT-PCR.

# <Rationale and Appropriateness of Endpoint>

DMD is a serious disease that occurs as a result of loss of dystrophin protein due to mutation of the dystrophin gene. Becker muscular dystrophy (BMD), like DMD, occurs due to mutation of the dystrophin gene, but a shorter dystrophin protein thought likely to have partial function is expressed, and thus it is a disease type with milder symptoms and progression. DS-5141b is expected to bind to the target sequence of the pre-mRNA of the dystrophin gene, produce exon 45-skipped mRNA, causing the production of shorter, but functional dystrophin protein like BMD, and thus delay the progression of DMD. Thus, expression of dystrophin protein in muscle tissue is likely to lead to delay the progression of DMD. At the same time, detection of exon 45-skipped mRNA is likely to be a useful index showing that this drug is exerting an action.

#### 9. SAFETY ENDPOINTS

The safety endpoints will be adverse events, laboratory data, body weight, vital signs, 12-lead electrocardiogram, and

#### 9.1 Definition of Adverse Event

An adverse event is any untoward or unintended sign (including abnormal changes in laboratory data and abnormal changes in vital signs), symptom or disease that occurs in a subject, whether or not they have a relationship with the study drug. Symptoms or diseases that occur before administration of the study drug will be considered complications, and will not be handled as adverse events. However, if a complication worsens during administration of the study drug, it will be handled as an adverse event, and the date when worsening was observed will be considered the date of onset of the adverse event.

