#### 4) 12-lead electrocardiogram

A standard 12-lead electrocardiogram will be recorded after the subject has been rested for ≥5 minutes in the decubitus position. The investigator or subinvestigator will judge the overall test result as "normal," "abnormal, not clinically significant" or "clinically significant finding" and record this on the case report form. If the judgment is "clinically significant finding," this will be handled as an adverse event, and details will be recorded on the case report form. However, abnormalities already observed before study drug administration that have not worsened after study drug administration will not be handled as adverse events.

<12-lead electrocardiogram observation points>

- Part 1
  - Day 1 (pre-dose, 2 hours and 6 hours post-dose), Day 2, Day 4, Day 8 (pre-dose, 2 hours and 6 hours post-dose), Day 9, Day 11, Day 15, Day 22, Day 36, Day 64
- Part 2

Day 1 (pre-dose, 2 hours and 6 hours post-dose), Day 2, Day 22 (pre-dose), Day 50 (pre-dose), Day 78 (pre-dose, 2 hours, 4 hours, 6 hours, and 8 hours post-dose), Day 79, Day 85, Day 92, Day 106, Day 134, Day 162

Part 2-Extension

Week 1/ Day 1 (pre-dose and 4 hours post-dose), Week 1/ Day 2,
Week 5/ Day 29 (pre-dose), Week 9/ Day 57 (pre-dose), Week 13/ Day 85
(pre-dose), Week 17/ Day 113 (pre-dose), Week 21/ Day 141 (pre-dose),
Week 25/ Day 169 (pre-dose), Week 29/ Day 197 (pre-dose),
Week 33/ Day 225 (pre-dose), Week 37/ Day 253 (pre-dose),
Week 41/ Day 281 (pre-dose), Week 45/ Day 309 (pre-dose),
Week 48/ Day 330 (pre-dose, 2 hours, 4 hours, 6 hours, and 8 hours post-dose),
Week 48/ Day 331, Week 49/ Day 337, Week 52/ Day 358

• Part 2-Extension-2

Week 1/ Day 1 (pre-dose and 4 hours post-dose), Week 1/ Day 2, Week 5/ Day 29 (pre-dose), Week 9/ Day 57 (pre-dose), Week 13/ Day 85 (pre-dose), Week 17/ Day 113 (pre-dose), Week 21/ Day 141 (pre-dose), Week 25/ Day 169 (pre-dose), Week 29/ Day 197 (pre-dose), Week 33/ Day 225 (pre-dose), Week 37/ Day 253 (pre-dose),

Week 41/ Day 281 (pre-dose), Week 45/ Day 309 (pre-dose), Week 48/ Day 330 (pre-dose, 2 hours, 4 hours, 6 hours, and 8 hours post-dose), Week 48/ Day 331, Week 49/ Day 337, Week 52/ Day 358

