# 6.4.2.2 Items to Be Performed During the Treatment Period (Day 1 to Day 14) and Follow-Up Period (Day 15 to Day 64) for Each Dose Level

The visit window for items performed on Day 15 and Day 22 is  $\pm 2$  days, and the visit window for items performed on Day 36 and Day 64 is  $\pm 7$  days.

- Checking the administration status of the study drug Whether the study drug was administered, date/time of study drug administration, dose level, actual dose (mg)
- 2) Investigating concomitant medications and concomitant therapy
- 3) Investigating adverse events
- 4) Body weight
  - <Observation point>

Day 15

- 5) Vital signs and clinical findings
  - <Observation point>

Day 1 (pre-dose and 1 hour, 2 hours, and 6 hours post-dose), Day 2, Day 4, Day 8 (pre-dose and 1 hour, 2 hours, and 6 hours post-dose), Day 9, Day 11, Day 15, Day 22, Day 36, Day 64

6) Blood tests and urinalysis

<Observation point>

Day 1 (pre-dose),\*8 Day 2, Day 4,\*8 Day 8 (pre-dose), Day 9, Day 11,\*8 Day 15, Day 36, Day 64

- 7) 12-lead electrocardiogram
  - <Observation point>

See 6.2

- 8) Blood collection
  - Pharmacokinetics

<Blood collection point>

See 6.7

- Anti-dystrophin antibody
  - <Blood collection point>

Day 15

- Anti-DS-5141b antibody
  - <Blood collection point>

Day 15

Blood cell dystrophin mRNA

<Blood collection point> Day 15

- 9) Urine collection
  - Urine protein

<Urine collection point>

Day 15

• Urine DS-5141b metabolites

<Urine collection point>

Day 9

#### 6.4.3 Part 2

## 6.4.3.1 Items to Be Performed Before the First Dose of Study Drug in Part 2

If subjects who have finished Part 1 continue to participate, the following will be performed from 14 days before the first dose of the study drug up to the day before the first dose of the study drug (Day 0). For subjects participating from Part 2, "6.4.1 Items to Be Performed After Registration up to the Day Before the First Dose of Study Drug (Day 0)" will be performed, and these tests will not be necessary.

- 1) Checking concomitant medications and concomitant therapy
- 2) Height and body weight
- 3) Vital signs and clinical findings
- 4) Blood tests and urinalysis
- 5) 12-lead electrocardiogram
- 6) MRI (only for subjects in whom MRI can be performed appropriately)

<Location of imaging>

MRI: Thigh

- 7) Motor function assessment\*9
- 8) Respiratory function assessment
- 9) Cardiac function assessment
- 10) Quantitative muscle strength assessment\*9
- 11) Blood collection

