# 6.4.3.2 Items to Be Performed During the Treatment Period (Day 1 to Day 84) and Follow-Up Period (Day 85 to Day 162)

The visit window for items performed on Day 8 to Day 92 is  $\pm 2$  days, and the visit window for items performed on Day 106, Day 134, and Day 162 is  $\pm 7$  days.

- Administration status of the study drug Whether the study drug was administered, date/time of study drug administration, dose level, actual dose (mg)
- 2) Investigating concomitant medications and concomitant therapy
- 3) Investigating adverse events
- 4) Body weight
  - <Observation point>
  - Day 29, Day 57, Day 85
- 5) Vital signs and clinical findings
  - <Observation point>
  - Day 1 (pre-dose and 1 hour, 2 hours, and 6 hours post-dose), Day 2, Day 8, Day 15, Day 22, Day 29, Day 36, Day 43, Day 50, Day 57, Day 64, Day 71, Day 78 (pre-dose and 1 hour, 2 hours, and 6 hours post-dose), Day 79, Day 85, Day 92, Day 106, Day 134, Day 162 (to be performed pre-dose on Day 8 to Day 78)
- 6) Blood tests and urinalysis
  - <Observation point>

Day 1,\*10 Day 2, Day 22, Day 50, Day 78,\*10 Day 85, Day 106, Day 134, Day 162 (to be performed pre-dose on Day 1 to Day 78)

7) 12-lead electrocardiogram

<Observation point>

See 6.2

8) MRI or CT

<Location of imaging>

Upper arm: MRI or CT (to confirm the location of muscle biopsy)

Thigh: MRI

<Investigation point>

To be performed once in the period from Day 85 to Day 99.

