# 6.4.5.2 Items to Be Performed During the Treatment Period (Week 1/ Day 1 to Week 48/ Day 336) and Follow-Up Period (Week 49/ Day 337 to Week 52/ Day 358)

The visit window for items performed on Week 2/ Day 8 to Week 50/ Day 344 is ±2 days, and the visit window for items performed on Week 52/ Day 358 is ±7 days. Subjects who complete 48 weeks of study drug administration in Part 2-Extension-2 and complete efficacy assessment after administration may participate in the long-term extension study. For subjects who participate in the long-term extension study, Week 52/ Day 358 will not be performed.

As a measure to prevent the spread of the novel coronavirus, self-administration will be allowed. Consent for self-administration will be obtained from the legally acceptable representative, and the guardian performing self-administration will be given training in the method of storing the study drug and the method of administering the study drug before self-administration starts.

- 1) Administration status of the study drug
  - Whether the study drug was administered, date/time of study drug administration, dose level, actual dose (mg), and checking the "Self-Injection Diary" if self-administration was performed
  - <Time points at which self-administration is possible>
  - Week 28/ Day 190, Week 30/ Day 204, Week 31/ Day 211, Week 32/ Day 218,
  - Week 34/ Day 232, Week 35/ Day 239, Week 36/ Day 246, Week 38/ Day 260,
  - Week 39/ Day 267, Week 40/ Day 274, Week 42/ Day 288, Week 43/ Day 295,
  - Week 44/ Day 302, Week 46/ Day 316, Week 47/ Day 323
- 2) Investigating concomitant medications and concomitant therapy
- 3) Investigating adverse events
- 4) Height and body weight
  - <Observation point>

\*13: To be performed twice.

Week 13/ Day 85, Week 25/ Day 169, Week 37/ Day 253, Week 48/ Day 330

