#### 9.4 Adverse Event Collection Period

The adverse event collection period will be as follows.

- From the first dose of the study drug at each dose level in Part 1 to the end of the follow-up period
- From the first dose of the study drug in Part 2 to the end of the follow-up period
- From the first dose of the study drug in Part 2-Extension to the end of the follow-up period in Part 2-Extension-2 (for subjects participating in the study from Part 2-Extension-2, from the first dose of the study drug in Part 2-Extension-2 to the end of the follow-up period in Part 2-Extension-2. For subjects participating in the long-term extension study, until the first dose of the study drug in the long-term extension study.)

All adverse events that occur during this period will be recorded on the case report form. Even outside the collection period, adverse events that the investigator or subinvestigator determines have a relationship with the study drug will be reported to the sponsor in the same way as during the collection period.

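### Section 9.1 counts worsening of a pre-existing symptom or disease as an adverse event only during administration, while section 9.4 collects adverse events to the end of follow-up

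*Combined protocol and SAP*

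**What the plan says.** Section 9.1 opens with a broad definition: any untoward sign, symptom or disease, related to the drug or not. It then removes what was there beforehand: "Symptoms or diseases that occur before administration of the study drug will be considered complications, and will not be handled as adverse events". One exception follows: "if a complication worsens during administration of the study drug, it will be handled as an adverse event". The phrase during administration is not defined there or elsewhere.

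Section 9.4 sets the collection period. For Part 2 it runs "From the first dose of the study drug in Part 2 to the end of the follow-up period", and Part 1 has the same rule per dose level. For subjects in the extensions it runs without a break from the first dose in Part 2-Extension to the end of follow-up in Part 2-Extension-2.

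The protocol separates dosing from follow-up in every part. The Part 1 schedule (6.4.2.2), for example, is headed by a "Treatment Period (Day 1 to Day 14) and Follow-Up Period (Day 15 to Day 64) for Each Dose Level". Sections 6.4.3.2, 6.4.4.2 and 6.4.5.2 do the same for the other parts.

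For the ECG, section 6.2 uses a different test: "abnormalities already observed before study drug administration that have not worsened after study drug administration will not be handled as adverse events". The same rule is given for a second test whose name is redacted. Section 9.3 makes a laboratory, vital-sign or other test result an adverse event if it leads to suspension, postponement or discontinuation of the drug, needs new intervention, or is judged clinically significant. It sets no time limit.

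**The concern.** The definition and the collection period do not cover the same span. If during administration means the treatment period, the single exception in 9.1 ends when follow-up begins, while 9.4 continues. A pre-existing symptom or disease that deteriorates in follow-up then has no route into the adverse event record unless it also produces a qualifying test result.

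Three consequences follow:

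- Section 9.2 defines a serious adverse event as an adverse event meeting listed criteria. Off-dosing worsening that needed hospital admission would, on this wording, not be a serious adverse event and would not trigger the prompt report in 9.7.2.
- It would be absent from the incidence and severity tables in 11.4.4.1.
- Similar worsening would be classified differently according to how it was detected, because 6.2 says after administration where 9.1 says during.

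The disease is progressive (section 1.1) and the nonclinical data describe slow elimination (section 1.2.3), so worsening after the last dose is worth capturing. Adverse events are a safety endpoint of a study whose first stated aim is safety.

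**Working it through.** The documents state no figure to reproduce. The check sets the two clauses against the schedule and counts days.

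**Inputs** (section headings; day counts inclusive)

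- Part 1, per dose level (6.4.2.2): treatment Days 1–14, follow-up Days 15–64.
- Part 2 (6.4.3.2): treatment Days 1–84, follow-up Days 85–162.
- Part 2-Extension and Part 2-Extension-2 (6.4.4.2, 6.4.5.2): treatment Days 1–336, follow-up Days 337–358.

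**Formula:** share off dosing = follow-up days / (treatment + follow-up days).

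| Part | Follow-up days | Total days | Share |
|---|---|---|---|
| Part 1, per dose level | 64 − 14 = 50 | 64 | 78.1% |
| Part 2 | 162 − 84 = 78 | 162 | 48.1% |
| Each extension | 358 − 336 = 22 | 358 | 6.1% |

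**Sensitivity to the counting rule**

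- From the day after the last dose (Days 8, 78 and 330): 56/64 = 87.5%, 84/162 = 51.9%, 28/358 = 7.8%.
- With the ±7-day window on the final visit: 43/57 to 57/71 = 75.4% to 80.3%; 71/155 to 85/169 = 45.8% to 50.3%; 15/351 to 29/365 = 4.3% to 7.9%.

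The extension figure is the planned schedule. Dosing in Part 2-Extension was temporarily discontinued (sections 1.2.6 and 3), and 9.4 keeps that interval inside the collection period for continuing subjects. Its length is not given.

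**Does another clause close the gap?**

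- 9.3 closes it for test results that meet one of its three criteria, at any time. It does not reach symptoms or diseases as such.
- 6.2 closes it for the ECG and one other test.
- The last sentence of 9.4, on related events outside the collection period, does not help: it presupposes an adverse event.
- The follow-up visit after withdrawal (6.6), 28 days after the last dose, asks about adverse events when the subject is off dosing, so the same wording applies.

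What remains is worsening of a pre-existing symptom or disease, off dosing, with no qualifying test result.

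**Weight of one event:** section 1.2.6 reports 7 treated subjects, so one subject is 1/7 = 14.3 percentage points in any row. All 7 had already reported an injection site reaction by 30 Aug 2019, so the study-wide proportion with any event cannot rise. What can change is incidence by system organ class or preferred term, severity, and serious events (1 of 7 at that date).

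**The case against.** The strongest reply is that during administration is undefined, and section 9.1 contrasts it with before administration. It can be read as any time after first dose, in which case nothing is excluded. That reading is possible, and it means the plan does not certainly exclude these events. It is not a defence of the text, since sites may read the phrase differently and classify the same event differently.

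Second, much worsening is caught elsewhere. A new sign or symptom in follow-up is an adverse event under the opening sentence of 9.1. Cardiac and renal deterioration may show on ECG, troponin T, cystatin C or urinalysis and enter through 6.2 or 9.3. Laboratory, vital-sign and ECG data are summarised over time whatever their adverse event status, and Part 2 functional assessments fall on Days 85–99, within follow-up. All of this stands, and it confines the gap to symptoms and diseases.

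Third, a reader might infer that 78% or 48% of worsening events are lost. The documents do not support that: these are shares of scheduled days, no event rate is given and no missed event is shown. Nor do they show that every subject has complications; the exclusion criteria remove several severe organ disorders.

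A reader might also infer substantial drug exposure through follow-up from the half-lives in section 6.7: 2^(−672/296) = 21% and 2^(−28/29) = 51% remaining at 28 days. The 296 hours is a monkey value and the 29 days belongs to another oligonucleotide, so neither measures exposure to this drug in these boys.

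Last, Part 2 was complete by 19 Mar 2018, so new wording alone cannot alter what was recorded in Parts 1 and 2. That is correct, and it is why the fix includes a record check.

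**Conclusion.** The mismatch between 9.1 and 9.4 is real, and no other clause removes it for worsening of a pre-existing symptom or disease without a qualifying test result. On the plain reading, such worsening off dosing is inside the collection period but is neither an adverse event nor a serious one.

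The time exposed is about 78% of scheduled days per Part 1 dose level, 48% in Part 2 and 6% in each extension, plus an interruption of unstated length for continuing subjects. The number of events affected cannot be estimated from the documents and may be zero.

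The conclusion assumes that during administration means the treatment period. If it means after first dose, the remaining fault is an undefined term. Either way 9.1 should be clarified. The stronger statement, that any worsening in follow-up goes uncounted, does not hold, because 9.3 and 6.2 cover test results.

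**What to change.** In 9.1, replace the condition on worsening with: *worsens at any time after the first dose of study drug within the collection period in 9.4*. This agrees with the test already used in 6.2. Carry the same wording into the case report form completion guideline. The span left uncovered then falls to zero in every part.

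Before database lock, ask the sites to check source records of the treated subjects (7 reported in section 1.2.6) for complication worsening dated off dosing, including the interruption between the two extensions. Source records are needed because section 6.3 lists only presence, ongoing status, findings and diagnoses for complications, with no date of later worsening. A query on the case report form alone may therefore find nothing.

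The cost is one phrase in the protocol, the matching guideline text and a record check at two sites. No dose, visit or procedure changes. The downside is that reported adverse event incidence may rise slightly, and the study report should say that events found by the check were added under the clarified definition.
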